- Leveling of these segments will be carried out using orthodontic wires sequentially, till 0.019" x 0.025" stainless steel archwire is reached.
- Segmented stiff 0.019" x 0.025" stainless steel archwire will be used to minimize the distal tipping and rotation of the molars. It will be extended from the maxillary second molar to the maxillary first premolar.
- In the first approach, a nickel titanium open coil spring will be inserted mesial to the maxillary first molar to provide distalizing force. In the second approach, two pieces of nickel titanium open coil springs will be inserted mesial to the maxillary first molar and mesial to the maxillary second molar.
- Mini screw anchorage system will be used as a mean of indirect anchorage.
- The patients will be seen every four weeks for reactivation until Class I molar relationship is obtained, as assessed clinically.

Methods of assessment:

- The rate of tooth movement will be analyzed using computer software on digital models obtained every four weeks. When a Class I molar relationship is obtained distalization will be considered achieved, which will be assessed clinically.
- Cone beam computed tomography (CBCT) will be taken for every patient pre-treatment and post-distalization.

Adverse event reporting

Anticipated adverse effects regarding the use of mini screw and its remedy

1. **Pain and discomfort:** If present, it may last 1–2 days and could be reduced by instructing the patient to use warm mouth rinse containing local anesthetic agent.
2. **Irritation to the buccal mucosa:** Bonding resin or a periodontal wound dressing could be applied to the head of the mini screw to smooth its surface and to minimize soft-tissue irritation.
3. **Inflammation around mini screw:** The screws need to be thoroughly cleaned. Mild infections can be controlled by using antiseptic mouthwash and by regular brushing.
4. **Mini screw mobility or failure:** The patient will be instructed to avoid manipulating the screw with fingers, tongue, or with foreign objects like pens. The mini screw could be tightened and left for 1–2 months with no loading, or light loading if necessary. If stability cannot be regained, the mini screw will be removed and replaced.

Statistical analysis

All gathered data will be tabulated and statistically analyzed.

References

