Document Date: June 23, 2022

Three Dimensional Assessment of Maxillary Molars Following Distalization Using Two Different Approaches

A Thesis
Submitted to Faculty of Dentistry
Ain-Shams University
In Partial Fulfillment of the Requirements of
Master's Degree in Orthodontics

Faculty of Dentistry
Ain Shams University
2022

Statistical analysis

Statistical analysis was performed with SPSS 20^{®*}, Graph Pad Prism^{®**}, and Microsoft Excel 2016^{***}.

All quantitative data were explored for normality by using Shapiro Wilk Normality test and presented as means and standard deviation (SD) values. All qualitative data were presented as frequency & percentage. All data were presented in (43) tables & (38) graphs.

Tests used:

- Comparisons 2 different groups was performed by using Mann Whitney test.
- Comparisons 2 successive follow ups periods was performed by using Paired t-test.
- Comparison between quantitative continuous data (Age & Duration) was performed by Independent t-test.
- Comparison between qualitative dichotomous data (Gender) was performed by Chi square test.
- Reliability test was performed by using Intra-class Correlation Coefficient (ICC).

* Statistical Package for Social Science, IBM, Armonk, NY, USA.

** Graph Pad Technologies, San Diego, CA, USA

*** Microsoft Co-operation, Redmond, WA, USA.

* All results presented as:

I. Normality test.

II. Baseline characteristics:

- A. Age.
- B. Gender.
- C. Duration
- D. Pretreatment measurements. (Appendix IV).

III. Measurements

The following measurements were carried for both group I and group II as well as in comparison between the two groups.

A. Skeletal measurements

- 1. Skeletal antero-posterior measurements.
- 2. Skeletal vertical measurements.

B. Dental measurements

- 1. Angular
- 2. Linear

C. Soft tissue measurements.

IV. Reliability: (Appendix V)

- A. Inter-observer.
- B. Intra-observer.

I. Normality test:

Exploration of the given data was performed using Shapiro-Wilk test and Kolmogorov-Smirnov test for normality. As Listed in (Table 11) and showed in (Figure 53), it was revealed that the significant level (P-value) was shown to be insignificant as P-value > 0.05 , which indicated that alternative hypothesis was rejected, and the concluded data originated from normal distribution (parametric data) resembling normal Bell curve in pre & post measurements while P value was significant in the difference between both groups which indicated nonparametric data.

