Table (11): Normality exploration of both groups regarding all measurements:

Measurements		Group I Single Coil Spring	Group II Double Coil Spring
Skeletal.	Pre	> 0.05	> 0.05
	Post	> 0.05	> 0.05
	Difference	$< 0.05^*$	$< 0.05^*$
Dental	Pre	> 0.05	> 0.05
	Post	> 0.05	> 0.05
	Difference	$< 0.05^*$	$< 0.05^*$
Soft tissue	Pre	> 0.05	> 0.05
	Post	> 0.05	> 0.05
	Difference	$< 0.05^*$	$< 0.05^*$

* Significant difference as $P < 0.05$

[figure not shown]
[figure not shown]

Figure (53): Scattered chart represents normal bell curve of normality test.

II. Baseline characterized:

1. Age:

In group I, minimum age was (18.4), maximum was (21.2), while mean \pm standard deviation was (19.42 ± 1.03) . In group II, minimum age was (18.08), maximum was (23.17), while mean \pm standard deviation was (20.7 ± 2.24) , as presented in table (12) and figure (54).

Comparison between both groups was performed by using Independent t-test which revealed insignificant difference between them as $P > 0.05$, as presented in table (12).

Table (12): Minimum, maximum, mean & standard deviation of age in both groups:

	Min	Max	M	SD	P value
G I	18.4	21.2	19.42	1.03	0.09
G II	18.08	23.17	20.7	2.24	

N: count

Min: minimum

Max: maximum

M: mean

SD: standard deviation

[figure not shown]

Figure (54): Bar chart showing mean of age in both groups.

2. Gender:

In gender all companions were performed by using Chi square test. In group I, male (16.67%) was significantly lower than female (83.3%) as $P < 0.05$, while in group II male (33.3%) was insignificantly lower than female (66.6%) as $P > 0.05$, as presented in table (13) and figure (55).

Also, comparison between group I & II reveled insignificant difference between them in both male & female as $P > 0.05$ as presented in table (13).

Table (13): Frequency & percentage of gender distribution in both groups:

Group	Male		Female		P value
	N	%	N	%	
Group I	2	16.67%	10	83.33%	0.001*
Group II	3	33.33%	6	66.67%	0.13
P value	0.34		0.34		

N: count

%: percentage

P: probability level which is significant at $P \leq 0.05$

[figure not shown]

Figure (55): Bar chart showing percentage of gender distribution in both groups

3. Duration:

In group I, minimum duration was (5.5 months), maximum was (9.73 months), while mean \pm standard deviation was (8.03 ± 2.9) . In group II, minimum duration was (4 months), maximum was (14.9 months), while mean \pm standard deviation was (10.59 ± 3.89) .

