Table (37): Mean & standard deviation of pretreatment, post treatment records and difference between them regarding transverse - linear dental measurements in group II:

Group II Transverse Linear Dental Measurements	pre		post		Difference		P value
	M	SD	M	SD	M	SD	
U4	17.45	2.12	18.04	2.02	0.60	1.95	0.387
U5	20.04	1.82	20.80	2.00	0.76	1.59	0.188
U6	23.01	1.76	23.66	1.35	0.65	1.15	0.130
U7	25.04	2.14	25.06	1.80	0.02	2.30	0.984

M: mean

SD: standard deviation

MD: mean difference

P: probability level which is significant at $P \leq 0.05$

[figure not shown]

Figure (79): Bar chart showing mean of pretreatment, post treatment records and difference between them regarding transverse - linear dental measurements in group II.

- **Comparison between both groups:**

Comparison between group I & II regarding difference between pretreatment & posttreatment records of transverse – linear dental measurements was performed by using Mann Whitney test which revealed insignificant difference between them regarding all measurements except U5 (Group I was significantly higher than group II) as $P < 0.05$, as presented in table (38) and figure (80).

Table (38): Comparison between both groups regarding transverse - linear dental measurements:

Difference Transverse Linear Dental Measurements	Group I		Group II		P value
	MD	SD	MD	SD	
U4	1.75	1.36	0.60	1.95	0.19
U5	2.01	1.11	0.76	1.59	0.04*
U6	1.43	0.98	0.65	1.15	0.09
U7	0.95	1.01	0.02	2.30	0.31

SD: standard deviation

MD: mean difference

P: probability level which is significant at $P \leq 0.05$

[figure not shown]

Figure (80): Bar chart showing comparison between both groups regarding transverse -linear dental measurements.

C. Soft tissue

- **Group I:**

In group I pretreatment records, post treatment records and difference between them regarding soft tissue measurements were presented in table (39) and figure (81,82).

Comparison between pretreatment & post treatment records was performed by using Paired t-test which revealed insignificant difference between them in all measurements as $P > 0.05$, as presented in table (39).

Table (39): Mean & standard deviation of pretreatment, post treatment records and difference between them regarding soft tissue measurements in group I:

Group I Soft tissue Measurements	Pre		Post		Difference		P value
	M	SD	M	SD	MD	SD	
Ls/E-line distance	2.72	1.27	2.81	0.74	0.10	0.70	0.643
Li/E-line distance	2.40	1.58	2.05	1.46	-0.36	0.96	0.226
NLA angle	97.44	12.44	98.61	13.17	1.17	3.37	0.253

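### Table 38 singles out U5 as the only tooth with a between-arm transverse difference, but one P of 0.04 beside 0.19, 0.09 and 0.31 does not show that the arms differ at U5 only

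*SAP*

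**What the plan says.** The SAP's list of tests gives one rule for comparing arms: "Comparisons 2 different groups was performed by using Mann Whitney test". In the section on transverse linear dental measurements, this test is applied tooth by tooth to the change from pretreatment to post-treatment. The text above Table 38 then reports an "insignificant difference between them regarding all measurements except U5 (Group I was significantly higher than group II").

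The first two rows of Table 38 read "U4 1.75 1.36 0.60 1.95 0.19" and "U5 2.01 1.11 0.76 1.59 0.04" (mean change and SD in Group I, mean change and SD in Group II, P). The P values for U6 and U7 are 0.09 and 0.31. The table gives no between-arm difference and no confidence interval. The SAP describes no comparison between teeth and no multiplicity adjustment.

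The Protocol's Procedure section puts the four teeth on one stiff steel segment: "It will be extended from the maxillary second molar to the maxillary first premolar".

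**The concern.** A reader of Table 38 will naturally conclude that the two spring arrangements differ transversely at the second premolar and not at the first premolar or the molars. Four separate tests cannot support that. A significant result at one tooth and non-significant results at others do not show that the teeth differ from one another. That needs a test of the difference between the arm effects, and none was done.

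The printed means make the contrast look doubtful. The gap at U4 is 92% of the gap at U5 (1.15/1.25), yet one is called insignificant and the other significant. U4 has the higher P mainly because its SDs are larger (1.36 and 1.95, against 1.11 and 1.59 at U5). At stake is how a side effect of the two approaches is described: as local to one tooth, or as an imprecisely estimated difference in the same direction at all four.

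**Working it through.** **Inputs.** Means and SDs come from Table 38. The arm sizes, 12 and 9, are the sums of the gender counts in Table 13. As a check on 9, paired t-tests on the Table 37 changes give 0.383, 0.189, 0.128 and 0.980 against the printed 0.387, 0.188, 0.130 and 0.984. As a check on 12, the SNB row of Table 15 gives t = 0.54/(1.36/√12) = 1.375 on 11 df, P about 0.20 against the printed 0.194. Tests are taken as two-sided.

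**The SAP's own figures.** A Mann-Whitney P cannot be rebuilt from means and SDs, so t-tests serve as a proxy (pooled / Welch, then printed): U4 0.127 / 0.153, 0.19; U5 0.047 / 0.064, 0.04; U6 0.110 / 0.121, 0.09; U7 0.224 / 0.283, 0.31. These are compatible with the table.

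**Between-arm gaps.** SE = √(s₁²/12 + s₂²/9), with Welch degrees of freedom. For U5, SE = √(0.103 + 0.281) = 0.62.

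| Tooth | Gap, Group I minus II (mm) | SE | Welch 95% CI |
|---|---|---|---|
| U4 | 1.75 - 0.60 = 1.15 | 0.76 | -0.48 to 2.78 |
| U5 | 2.01 - 0.76 = 1.25 | 0.62 | -0.08 to 2.58 |
| U6 | 1.43 - 0.65 = 0.78 | 0.48 | -0.23 to 1.79 |
| U7 | 0.95 - 0.02 = 0.93 | 0.82 | -0.89 to 2.75 |

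All four gaps have the same sign, and each interval contains the other three estimates. The pooled interval for U5 is 0.02 to 2.48, so U5 is borderline and depends on the method.

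**Is U5's gap different from the others?** This depends on the within-patient correlation r between teeth, which is not printed. I assumed a common r and varied it. For two teeth, the variance of the contrast within an arm is s₅² + s_k² - 2r·s₅·s_k, divided by that arm's n and summed over arms. For U5 against U4 at r = 0.5: 1.572/12 + 3.230/9 = 0.490, SE 0.70, contrast 0.10 mm, P 0.89. For r from 0 to 0.9:

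- U5 - U4: 0.10 mm, P 0.92 down to 0.77
- U5 - U6: 0.47 mm, P 0.56 down to 0.12
- U5 - U7: 0.32 mm, P 0.76 down to 0.43
- U5 minus the mean of the other three: 0.30 mm, P 0.69 down to 0.24
- all four gaps equal (chi-square on 3 df): P 0.94 down to 0.34

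**Multiplicity over the four teeth.** Holm: U5 4 × 0.04 = 0.16; U6 3 × 0.09 = 0.27; U4 2 × 0.19 = 0.38; U7 0.38.

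**Mean of the four teeth.** Group I 6.14/4 = 1.535 mm; Group II 2.03/4 = 0.5075 mm; difference 1.03 mm. Welch: 0.11 to 1.95 (P 0.032) at r = 0.2; -0.12 to 2.17 (P 0.074) at r = 0.5; -0.30 to 2.36 (P 0.119) at r = 0.8.

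**The case against.** The strongest reply is that the sentence only lists which P values fall below 0.05, and lists them correctly. The SAP nowhere states that U5 behaves differently from its neighbours. That stands. The fault lies in offering the list as the result of the comparison, with no estimate or interval to prevent the one-tooth reading.

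A reader might go further and infer that the arms differed by a uniform 1 mm or so along the whole segment. The documents do not support that:

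- The gaps at U6 and U7 are 62% and 74% of U5's (0.78/1.25 and 0.93/1.25). At r = 0.5 the U5 - U6 contrast has a Welch interval of about -0.74 to 1.68 mm. Failing to separate the teeth with 21 patients does not show that they are alike.
- The segment mean is itself uncertain. A shared stiff wire suggests a fairly high r, and from r = 0.5 upwards the Welch interval includes zero.
- The segment does not move as one unit. In Tables 30 and 31 the U5 tip moves forward (1.40 and 1.88 mm) while the first molar cusp moves back (-3.78 and -4.51 mm). The approaches also differ in where the springs sit. Tooth-level reporting is therefore reasonable, and a mean over premolars and molars chosen after seeing the data should not replace it.

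Nor is a U5-specific effect ruled out. If r were about 0.98, U5 against the other three would give a Welch P of 0.037. Table 26 also stars U5 alone, for rotation (P 0.009). That is a different measurement and does not settle this one, but it is a reason not to deny an effect at U5.

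Finally, other between-arm tables use similar exception wording, and a general multiplicity adjustment would remove this star. It would leave a verdict of no difference at any tooth, still without estimates and still without the comparison between teeth.

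**Conclusion.** The transverse results do not support a difference confined to U5. Group I has the larger mean change at all four teeth, by 0.78 to 1.25 mm, and every Welch interval includes zero. U4's gap is within 0.10 mm of U5's. No contrast of U5 with the other teeth reaches P 0.05 for r between 0 and 0.9, and U5's printed P becomes 0.16 under Holm.

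This rests on arm sizes of 12 and 9, on t-based intervals standing in for the rank test, and on an assumed common correlation. The reading changes only at correlations well above 0.9. The patient-level data would replace the assumption about r. The conclusion is limited to what Table 38 can claim: it establishes neither a U5-only effect nor a segment-wide one.

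**What to change.** In Table 38, print the between-arm difference at each tooth with its 95% CI. From the patient-level data, fit one model with arm, tooth and arm-by-tooth terms, patient as a random effect and unequal SDs allowed between arms, and report the arm-by-tooth test.

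Replace the sentence that excepts U5 with one saying that the mean transverse change was larger in Group I at all four teeth and that the estimates are imprecise. Claim a U5-specific difference only if the arm-by-tooth term supports it.

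A segment-mean comparison may be added if it is labelled post hoc and given as an estimate with its interval (about 1.03 mm; roughly -0.12 to 2.17 if r is 0.5). It should not be presented as an established difference or take the place of the tooth-level results.

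The cost is one extra analysis on data already held, one reworded paragraph and the loss of a starred result.
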